3. BACKGROUND AND RATIONALE

3.1 Introduction

Knee chondral lesions are tremendously common. Chondral lesions documented in arthroscopies in the years 1989-2004 range from 59% to 63% (7). Outerbridge Grade 2 was the most frequent grade of the cartilage lesion at 42% (7). Arthroscopic chondroplasty allows removal of loose and damaged cartilage which minimizes synovial irritation and mechanical impingement (2). Two techniques for chondroplasty are radiofrequency (RF) and mechanical debridement (MD).

A 10-year randomized controlled study by Spahn et al., concluded that bipolar temperature controlled RF treatment at 50 degrees seemed superior to mechanical debridement in their short and medium term clinical outcomes and the progression of knee osteoarthritis (5). Subjects in the RF treatment group achieved a higher activity level 1 and 4 years after surgery compared to the MD treatment group (5). The time to required revision in the MD treatment group was 62.5 months with a rate of revision of 60.0% in comparison to 94.1 months and 23.3% in the RF treatment group (5).

A study by Lotto et al., showed thermal chondroplasty using radiofrequency energy (RFE) produced a larger depth of cellular death than mechanical debridement (MD) (3). Yet, RFE resulted in less healthy cartilage removal than MD (3). Lotto et al.'s results showed greater arthroscopic smoothing with less passes using RFE compared to MD (3).

Current safety concerns regarding RF treatment include the possibility that it contributes to the development of osteonecrosis. A prospective clinical trial by Turker et al., found no increase in the incidence of subchondral osteonecrosis with the addition of either mechanical or radiofrequency chondroplasty during arthroscopic meniscectomy (6). Similarly, of the 60 patients treated for grade III femoral chondral lesions by Barber and Iwasko (1), no osteonecrosis was observed at the 12 month postoperative MRI.

A systematic review by Papalia et al. concluded that RFE is efficient and safe for the surgical treatment of chondral lesions, specifically Outerbridge Grade 2 and 3 lesions (4). Grade 4 lesions were found to be too advanced to respond positively to debridement (4). The systematic review of past studies comparing RFE to MD found noticeable similarities to aims and design with a lack of randomization (4).

Additional randomized controlled studies are needed to prove that radiofrequency-based debridement is not inferior to mechanical debridement for the treatment of articular cartilage lesions. The primary objective of the proposed study is to evaluate the efficacy of RF debridement vs. MD for subjects requiring treatment of multiple chondral lesions in addition to a partial medial meniscectomy. Secondary objectives include evaluating imaging and additional subjective and objective clinical outcomes.

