1. STUDY OBJECTIVES

1.1 Study Purpose

The purpose of this study is to evaluate the changes in clinical and imaging outcomes following arthroscopic treatment of chondral lesion(s) by Radiofrequency-Based debridement or Mechanical Debridement in subjects 18-50 years of age.

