1.2 Primary Objective

The primary objective is to evaluate the efficacy of Radiofrequency-Based debridement vs. Mechanical Debridement for the treatment of articular cartilage lesions.

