4. PROCEDURES

4.1 Research Design

This is a non-inferiority, prospective, single blinded, randomized, single-center study design with enrollment of 82 randomized subjects (to assure 70 subjects complete the study). The sample size of 82 participants was calculated from a power analysis. The study was powered to detect at least a seven point change in KOOS pain score based on achieving 80% statistical power to detect a non-inferiority margin. Study duration will be until the last subject enrolled reaches 52 weeks post-operative.

The 82 randomized subjects will be randomized at a 1:1 ratio into the Werewolf Coblation wand treatment group or mechanical debridement treatment group. Subjects will be blinded to their treatment assignment until they complete all study visits. Upon withdraw from the study, termination from the study, or new or recurrent symptoms requiring a subsequent arthroscopy, the blinded assignment will be revealed to the subject.

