4.5 Detailed Study Visits

Screening

- Confirm written informed consent prior to screening procedures
- Inclusion/exclusion criteria
- Physical assessment by surgeon – IKDC objective
- Demographics
- Medical and surgical history

- X-rays unless provided (must be less than 3 months old)
- MRI unless provided (must be less than 3 months old)
- Patient reported outcomes
 - KOOS, VAS, IKDC subjective, Marx

Date of surgery

- Arthroscopic inclusion/exclusion criteria
 - No articular cartilage lesion present that requires treatment
 - Evidence of previous chondral treatment not noted at screening
 - Chondrocalcinosi
- Randomization
- Surgery performed

10 days (7 days-14 days post op)

- Explanation of the weekly online data to be collected on RedCap
 - KOOS activity, VAS, return to work/activity (WPAI V2.0). [To be completed weekly from 1 week post op to 6 post op]
- Physical assessment by surgeon – IKDC objective
- Patient reported outcomes
 - KOOS, VAS, IKDC subjective, Marx

6 weeks (\pm 5 days)

- Physical assessment by surgeon – IKDC objective
- Patient reported outcomes
 - KOOS, VAS, IKDC subjective, Marx

6 months (\pm 14 days)- To be completed in RedCap

- Patient reported outcomes
 - KOOS, VAS, IKDC subjective, Marx

12 months (\pm 28 days)

- Physical assessment by surgeon – IKDC objective
- Patient reported outcomes
 - KOOS, VAS, IKDC subjective, Marx
- X-rays (merchant view, AP and PA Rosenberg)
- MRI

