5.3 Inclusion Criteria

Subjects MUST meet ALL of the following criteria to be included in the study:

- Given written informed consent on the IRB approved consent form specific to the study, prior to study participation
- 18-50 years old
- Male or Female
- Suspected chondral damage in the following locations where debridement is indicated:
 - Medial femoral condyle
 - Lateral femoral condyle
 - Trochlea
 - Patella
- < 30% joint space narrowing as seen on x-ray (merchant view, AP and PA Rosenberg)
- 1 or more chondral lesion(s) as noted on MRI
- Concomitant procedures are allowed unless noted in the exclusion criteria

5.4 Exclusion Criteria:

- Previous chondral treatment in the same compartment (prior debridement and lavage performed more than *three* months prior to baseline are acceptable)
- Focal chondral defect indicated for concomitant procedures (i.e., microfracture, ACI, MACI, OATs)
- Concomitant procedures that are not allowed:
 - Lateral retinacular release
 - Excision of osteophytes
 - Subchondroplasty
 - Manipulation under anesthesia
 - ACL reconstruction
 - Quad tendon repair
 - Patellar tendon repair
 - Patellar tendon debridement
 - Multiligament reconstruction
- Pregnant and/or intending to become pregnant during this study period

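### Does the sentence in Protocol 3.1 about multiple lesions plus partial medial meniscectomy give the trial a second, conflicting target population?

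*Protocol*

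**What the plan says.** The protocol describes its subjects in several places.

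- Section 1.1, Study Purpose: "arthroscopic treatment of chondral lesion(s) by Radiofrequency-Based debridement or Mechanical Debridement in subjects 18-50 years of age". The bracketed plural allows for a single lesion, and meniscectomy is not mentioned.
- Section 1.2, the formal objective: "The primary objective is to evaluate the efficacy of Radiofrequency-Based debridement vs. Mechanical Debridement for the treatment of articular cartilage lesions". It gives no minimum number of lesions and no accompanying procedure.
- Section 3.1, end of the Introduction: one sentence says that randomised evidence is needed to show that radiofrequency is "not inferior to mechanical debridement for the treatment of articular cartilage lesions". The next restates the primary objective for "subjects requiring treatment of multiple chondral lesions in addition to a partial medial meniscectomy".
- Section 4.5, check at arthroscopy before randomisation: the only finding about lesion number is "No articular cartilage lesion present that requires treatment". Meniscectomy is not part of the check.
- Section 5.3, Inclusion Criteria: "1 or more chondral lesion(s) as noted on MRI", and "Concomitant procedures are allowed unless noted in the exclusion criteria". Meniscectomy is not on the list of barred procedures in 5.4.

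Outside that one sentence in 3.1, meniscectomy appears only in accounts of cited studies and in the reference list.

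**The concern.** Section 3.1 does not present its sentence as loose context. It calls it the primary objective of the proposed study, and it departs from sections 1.1, 1.2 and 5.3 on two counts: the number of lesions and the accompanying meniscectomy.

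A non-inferiority conclusion has to be attached to a defined population. If 3.1 were the true target, the eligibility criteria would not deliver it, because an unknown share of the enrolled subjects would fall outside. A broad result reported under the 3.1 wording would be described as applying to a group that the sample represents only in part. The narrow reading is also not absurd: the ten-year randomised comparison of the same two techniques, summarised in 3.1, has concomitant medial meniscectomy in its title in the reference list.

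**Working it through.** **Step 1. Compare the statements.**

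| Place in the protocol | Number of lesions | Meniscectomy | Single lesion, no meniscectomy |
|---|---|---|---|
| 1.1 Purpose | one or more | not mentioned | fits |
| 1.2 Primary objective | no number given | not mentioned | not ruled out |
| 3.1, penultimate statement of need | no number given | not mentioned | not ruled out |
| 3.1, restated objective | multiple | required | outside |
| 4.5 Check at arthroscopy | at least one needing treatment | not mentioned | passes |
| 5.3 and 5.4 Eligibility | at least one on MRI | neither required nor barred | eligible |

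One row stands apart. *One or more* is explicit in 1.1 and 5.3 and follows from 4.5, while 1.2 gives no number. That meniscectomy is permitted is an inference from 5.3 and 5.4 alone.

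**Step 2. Ask which statements do any work.** Sections 4.5 and 5.3 to 5.4 decide who is randomised. Section 2 sets the endpoints and section 4.1 the design and sample size. None uses lesion multiplicity or meniscectomy. Deleting the two conditions from 3.1 would leave every eligibility decision, allocation and measurement as it is.

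**Step 3. Check whether a trial figure depends on the narrow population.** Section 4.1 randomises 82 "to assure 70 subjects complete the study".

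- Implied loss: (82 − 70)/82 = 12/82 = 14.6%. Conversely, 70/(1 − 12/82) = 82.
- The section gives 80% power and seven points on KOOS pain, but no SD and no alpha, so the 70 cannot be rederived from stated inputs. With 35 per arm and a true difference of zero, the implied SD is 7 × √(35/2)/(z(1−α) + z(0.80)). That is about 10.5 at one-sided 0.025 and about 11.8 at one-sided 0.05.
- No lesion count or meniscectomy rate enters this calculation. The wording in 3.1 moves neither 82 nor 70.

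**Step 4. What an analysis of the narrow group alone would give.** The protocol plans no such analysis; this only bounds the worst reading. Let q be the share of the 70 completers with multiple lesions and a partial medial meniscectomy. Then n = 70q, the confidence interval widens by 1/√q, and power = Φ(d√q − z(1−α)), with d = z(1−α) + z(0.80). So d = 1.645 + 0.842 = 2.487 at one-sided 0.05, and 1.960 + 0.842 = 2.802 at one-sided 0.025.

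| Assumed q | n | Interval width ratio | Power, one-sided 0.05 | Power, one-sided 0.025 |
|---|---|---|---|---|
| 0.80 | 56 | 1.12 | 71.9% | 70.7% |
| 0.50 | 35 | 1.41 | 54.5% | 50.8% |
| 0.25 | 17.5 | 2.0 | 34.4% | 28.8% |

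For example, at q = 0.50 and one-sided 0.05: 2.487 × 0.7071 − 1.645 = 0.114, and Φ(0.114) = 54.5%.

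The shares and alphas are assumptions. The table also takes the subset to have the same SD as the whole sample and balanced arms, a true difference of zero, and the 80% power to hold at 70 completers. Any subgroup of the same size would give the same numbers, so they say nothing specific about this sentence.

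**The case for a change.** The best case for a change is that the protocol labels two different statements as its primary objective, that nothing in it reconciles them, and that correcting one sentence costs almost nothing. An analysis plan would not normally correct the introduction of a protocol, and with the meniscectomy trial among the sources one cannot be certain that the narrow wording was an accident.

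The textual point stands in full: the two statements differ and should ideally agree. What does not stand is the consequence. A reader who has to choose between a section headed Primary Objective, supported by the eligibility criteria, and a sentence in the background has a clear order of precedence. It also goes too far to say that the trial cannot inform the 3.1 population. That population is a subset of those eligible, so the overall result bears on it unless the treatment effect varies with lesion number or meniscectomy, and the documents give no reason to expect that. What the trial lacks is a powered estimate for the subset alone, which the protocol never promises.

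Recording lesion number and meniscectomy would help describe the sample. It would not alter the primary comparison, and the inconsistency does not call for it.

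**Conclusion.** The inconsistency is genuine, but it is clerical and confined to one background sentence. Aligning that sentence with section 1.2 would alter no eligibility rule, endpoint, sample-size figure, error rate or planned comparison. The effect on the trial's own figures is zero. The reduced power shown for the narrow group belongs to an analysis nobody has proposed.

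This assumes that the broad population is the intended one. The protocol does not say so in as many words, but the formal objective and the criteria that govern enrolment both point that way. If the sponsor did intend the narrow population, the question would become one of eligibility rather than wording; nothing in the operative sections suggests it. Analysts can state the non-inferiority conclusion for the subjects enrolled under 5.3 and 5.4, and the sentence in 3.1 can be corrected as housekeeping.

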3.2 Study Device

The Smith and Nephew WEREWOLF COBLATION System is indicated for all soft tissue types in the knee. The WEREWOLF COBLATION System is a FDA cleared bipolar, radiofrequency electrosurgical system designed for use in orthopaedic/arthroscopic surgical procedures.

The WEREWOLF™ Controller and FLOW 50™ Wand obtained FDA 510(k) clearance (K162074) on August 22, 2016. Health Canada clearance is pending. The System consists of the following components:

1. A bipolar radiofrequency Controller with Integrated Fluid Outflow Regulator;
2. A non-sterile, reusable wired Foot Control and Power Cord
3. Sterile, disposable, single-use COBLATION Wands

3.3 Mechanism of Action

Smith & Nephew distributes COBLATION devices for ablation, resection, and coagulation of soft tissue and hemostasis of blood vessels in arthroscopic and orthopaedic procedures.

The FLOW 50 Wand is powered by the WEREWOLF Controller. This system uses a controlled radiofrequency-based plasma process (with the trademark 'COBLATION'). In this process, radiofrequency energy is used to excite the water molecules in a conductive medium, such as an electrolyte (saline) solution, to generate excited radicals within precisely focused plasma. The energized particles in the plasma have sufficient energy to break molecular bonds (16-18), excising or dissolving (i.e. ablating) soft tissue at relatively low temperatures (typically 40°C to 70°C). This technology is a radiofrequency-based technique but its mechanism of action is a chemical process and not a function of the radiofrequency energy itself.

The FLOW 50 Wand utilizes the Ambient™ feature which provides accurate ($\pm 3^\circ\text{C}$) real-time temperature monitoring of the intra-articular irrigating fluid.

These devices also provide the capability for hemostasis, typically delivered through devices that can also coagulate bleeding vessels.

4. PROCEDURES

4.1 Research Design

This is a non-inferiority, prospective, single blinded, randomized, single-center study design with enrollment of 82 randomized subjects (to assure 70 subjects complete the study). The sample size of 82 participants was calculated from a power analysis. The study was powered to detect at least a seven point change in KOOS pain score based on achieving 80% statistical power to detect a non-inferiority margin. Study duration will be until the last subject enrolled reaches 52 weeks post-operative.

The 82 randomized subjects will be randomized at a 1:1 ratio into the Werewolf Coblation wand treatment group or mechanical debridement treatment group. Subjects will be blinded to their treatment assignment until they complete all study visits. Upon withdraw from the study, termination from the study, or new or recurrent symptoms requiring a subsequent arthroscopy, the blinded assignment will be revealed to the subject.

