2. STUDY ENDPOINTS

2.1 Primary Endpoint

The primary endpoint is to evaluate the change in Knee and Osteoarthritis Outcome Scores (KOOS) activity subscale at Week 52 post-operative compared to baseline

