4.4 Measurement/Instrumentation

The change in the KOOS activity subscale will be the primary study endpoint. Secondary outcomes include time to return to work/activity and time to return to no pain. Baseline MRI will be compared to MRI at 52 weeks to evaluate knee morphology, cartilage signal, osteophytes, bone marrow edema, subarticular cysts, effusions and loose bodies. The international cartilage repair score will be used.

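### Section 4.1 states the trial's 80% power for the KOOS pain score, but Sections 2.1 and 4.4 make the KOOS activity subscale primary

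*Protocol*

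**What the plan says.** Section 4.1 (Research Design) describes a non-inferiority trial randomising 82 subjects 1:1 so that 70 complete. Its only account of the power calculation is this: "The study was powered to detect at least a seven point change in KOOS pain score based on achieving 80% statistical power". The rest of that sentence mentions a margin for non-inferiority but gives it no value of its own.

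Section 2.1 (Primary Endpoint) sets the primary endpoint as "change in Knee and Osteoarthritis Outcome Scores (KOOS) activity subscale at Week 52 post-operative compared to baseline". Section 4.4 (Measurement/Instrumentation) repeats it: "The change in the KOOS activity subscale will be the primary study endpoint".

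Section 4.5 (Detailed Study Visits) lists the measures for weekly online collection up to week 6 as "KOOS activity, VAS, return to work/activity (WPAI V2.0"; activity is the only KOOS subscale picked out there. The full KOOS is collected at screening and at every follow-up visit.

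**The concern.** A power statement should refer to the primary test. Here it refers to a different subscale of the same instrument. KOOS pain is not a primary or secondary endpoint in Sections 2.1, 2.2 or 4.4. Pain may be a one-word slip for activity, or the calculation may really have been done on pain. The text does not let a reader tell which.

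The mismatch matters more in a non-inferiority trial than in a superiority trial. The seven points are the only number in the protocol that could be the margin, and they too are attached to pain. Read literally, the decisive comparison has neither a stated power nor a stated margin. There is also a risk at the reporting stage: if the protocol can be read as supporting either subscale, the choice could be made after results are known.

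**Working it through.** **1. The passages side by side**

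| Protocol section | KOOS subscale named | Role |
|---|---|---|
| 2.1 | Activity | Primary endpoint, change from baseline to Week 52 |
| 4.4 | Activity | Primary endpoint |
| 4.5 | Activity | Weekly online collection |
| 4.1 | Pain | Seven points, 80% power, basis of the 82 |

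Section 2.2 lists pain only through the VAS. Section 4.4 adds time to return to no pain. Neither is KOOS pain. No sentence links a pain-based calculation to the activity subscale. The contradiction is established here and needs no arithmetic.

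**2. Can the plan's own figure be reproduced?**

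Inputs from Section 4.1: 82 randomised, 70 completers, 1:1 allocation, 80% power, seven points. The protocol states no SD, alpha or sidedness.

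- Implied attrition: (82 − 70)/82 = 12/82 = 14.6%, and 70/(1 − 0.146) rounds up to 82. The step from 70 to 82 is coherent.
- The 70 itself can be neither reproduced nor refuted, because it depends on the unstated SD and alpha.

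**3. What would have to be true of the activity subscale**

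Assumptions, none stated in the protocol for KOOS activity: margin 7, true difference 0, two-sample t-test on change, 35 evaluable subjects per arm (70/2), and one-sided alpha of 0.05 or 0.025.

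Power = P(T > t(1−α, 68)), where T is non-central t with 2 × 35 − 2 = 68 degrees of freedom and non-centrality 7 / (SD × √(2/35)).

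Solving for the SD that gives exactly 80%:

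- one-sided 0.05: SD = 11.66, so the detectable margin is 7/11.66 = 0.60 SD
- one-sided 0.025: SD = 10.30, so the detectable margin is 7/10.30 = 0.68 SD

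The normal approximation, SD = 7 / [(z(1−α) + z(0.80)) × √(2/35)], gives 11.78 and 10.45, which agrees closely.

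| Assumed SD of change | Power, one-sided 0.05 | Power, one-sided 0.025 | Margin for 80% power, 0.05 | Margin for 80% power, 0.025 |
|---|---|---|---|---|
| 9 | 94.3% | 89.4% | 5.40 | 6.11 |
| 10 | 89.5% | 82.3% | 6.00 | 6.79 |
| 12 | 78.0% | 67.2% | 7.20 | 8.15 |
| 15 | 61.3% | 48.6% | 9.01 | 10.19 |
| 18 | 48.6% | 36.1% | 10.81 | 12.23 |

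**4. Sensitivity to the number analysed**

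If all 82 were evaluable (41 per arm), the SD limits for 80% power rise to 12.64 and 11.18. Power at SD 12 becomes 83.5% (one-sided 0.05) or 74.2% (one-sided 0.025).

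The table shows how strongly power depends on the SD and margin of whichever subscale is tested. It does not measure the gap between pain and activity. That would need the SD of both subscales, and the protocol gives neither.

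**The case against.** The strongest reply is that this is probably a typing slip. Three sections point to activity and a single word in Section 4.1 points to pain. KOOS is collected in full at every visit, so no endpoint data are lost on either reading, and nothing shows that 82 is wrong. All of that is true, and it bears on how small the repair may be. It does not let a reader conclude that the calculation was done on activity.

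A second objection is that the power table would be identical if Section 4.1 had said activity. What drives it is the missing SD and alpha, which a protocol may leave to a statistical analysis plan. This stands: the table is illustrative and does not measure the error. It also borrows seven points as the margin for activity, which is the very link the protocol fails to make, so that too is only an assumption. The number analysed is likewise open to two readings, and at one-sided 0.05 with SD 12 the choice between 35 and 41 per arm moves power across 80%.

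The objection about the analysis plan does not dispose of the point itself. The complaint is not that detail is absent, but that one protocol section contradicts two others. An analysis plan could restate the calculation, but Section 4.1 would still disagree with Sections 2.1 and 4.4.

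**Conclusion.** The concern holds. As written, the only sample-size justification refers to an outcome that the protocol does not make primary, so the 80% is not a statement about the primary non-inferiority test. This has to be corrected, because it touches both the primary endpoint and the only candidate for the margin.

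The size and direction of any effect on power cannot be determined from the protocol. Under the assumptions listed, power on activity reaches 80% only if the SD of change is no more than 10.3 to 11.7 with 35 per arm, or 11.2 to 12.6 with 41 per arm, depending on alpha. True power could be above or below the stated 80%. The conclusion that the sections conflict depends on none of these assumptions.

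**What to change.** Name the same KOOS subscale in Sections 2.1, 4.1 and 4.4.

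- **Activity stays primary and pain was a slip:** confirm from the original calculation that it was done on activity, and correct the word in Section 4.1.
- **Activity stays primary and the calculation was done on pain:** redo it for change in KOOS activity at Week 52 with about 70 evaluable subjects and a margin justified for that subscale. State in Section 4.1 the power that the planned 82 randomised and 70 completing subjects deliver.
- **Pain was the intended primary:** amend Sections 2.1 and 4.4 instead, before anyone examines outcome data by arm. That condition is more useful than a reference to unblinding, because Section 4.1 describes only the subjects as blinded.

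The cost is a check or a recalculation, plus a wording amendment. The fix does not in itself require more enrolment. If the restated power falls below 80%, the sponsor must decide whether to accept it or revisit the sample size, and that cannot be judged until the calculation has been checked.
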